9.4.2 Pharmacokinetic Statistical Methodology

The PK parameters will be statistically analysed, listed and summarized by diabetic type and overall.

Log-transformed PK parameters (such as C_{max} and AUC) will be evaluated in a linear mixed-effects model with fixed effects for treatment, period, and sequence, and a random effect for patient. The treatment differences will be back-transformed to present the ratios of geometric means and the corresponding 90% confidence intervals (CIs).

Example SAS code:

```
proc mixed data=test covtest alpha=0.1;
  by parameter;
  class treatment patient period sequence;
  model log_pk = treatment period sequence / ddfm=kr alpha=0.1;
  random patient;
  lsmeans treatment / pdiff cl alpha=0.1;
  ods output lsmeans=lsmeans;
  ods output diffs=diffs;
  ods output covparms=cov;
run;
```

The t_{max} will be analyzed using the Wilcoxon signed-rank test. Estimates of the median difference based on the observed medians, 90% CIs, and p-values from the Wilcoxon test will be calculated.

Exploratory analyses may be performed for other PK parameters as deemed appropriate.

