Procedure	Days -28 to -2	Day -1	Day 1	3 to 14 days	Day -1	Day 1	Within 28±2 days after last study treatment		
Urine Drug Screen	X								Additional tests can be done at the discretion of the investigator.
PK (Glucagon)			Pre-hypoglycemia induction, Predose, 5, 10, 15, 20, 25, 30, 40, 50, 60, 90, 120, 240 min			Pre-hypoglycemia induction, Predose, 5, 10, 15, 20, 25, 30, 40, 50, 60, 90, 120, 240 min	X	X	Sampling times are relative to the time of study treatment administration (0 min). Predose time point will be between insulin infusion stop and study treatment.
Plasma Glucose for PD			Pre-hypoglycemia induction, -5, Predose, 5, 10, 15, 20, 25, 30, 40, 50, 60, 90, 120, 240 min			Pre-hypoglycemia induction, -5, Predose, 5, 10, 15, 20, 25, 30, 40, 50, 60, 90, 120, 240 min			-5 mins = stop insulin infusion. Sampling times are relative to the time of study treatment administration (0 min). Predose time point will be between insulin infusion stop and study treatment.
Genetic Sample (Stored)		X							Single sample for pharmacogenetic analysis taken prior to/on Period 1 Day -1.

	Screening		Period 1	Wash out		Period 2	Follow-up/ED	Additional Follow-up for TE ADA ^a	Comments
Procedure	Days -28 to -2	Day -1	Day 1	3 to 14 days	Day -1	Day 1	Within 28±2 days after last study treatment		
Anti-glucagon Antibodies			Pre-hypoglycemia induction				X	X	In the event of drug hypersensitivity reactions (immediate or non-immediate), samples will be collected as close to event onset as possible, at event resolution, and 30 days following the event. Patients with TE ADA at follow-up/ED will undergo additional follow-up. Refer to Section 9.7.1 for details.
Health Outcome Instruments									
Clarke Hypoglycemia Awareness Survey		X							
Nasal and Non-nasal Score Questionnaire			Pre-hypoglycemia induction, 15, 30, 60, 120 min			Pre-hypoglycemia induction, 15, 30, 60, 120 min			Sampling times are relative to the time of study treatment administration (0 min). Questionnaire will be collected in both LY900018 and IMG treatment groups in both periods.

	Screening		Period 1	Wash out		Period 2	Follow-up/ED	Additional Follow-up for TE ADA ^a	Comments
Procedure	Days -28 to -2	Day -1	Day 1	3 to 14 days	Day -1	Day 1	Within 28±2 days after last study treatment		

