4.2 Secondary

The secondary objectives are:

- To compare the safety and tolerability of 3 mg LY900018 with 1 mg IMG
- To characterize the PK profile of 3 mg LY900018 compared to 1 mg IMG
- To characterize the PD profile of 3 mg LY900018 compared to 1 mg IMG

Final, 01 Feb 2018 Page 6 of 26

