7. SAMPLE SIZE JUSTIFICATION

Seventy five patients may be enrolled in order to have at least 66 patients (at least 30 patients with T1DM and T2DM, respectively) complete the study. For purposes of this study, a completer is defined as a patient who completes both periods with evaluable primary outcome. If patients discontinue from the study before completion of both periods with evaluable primary outcome for any reason, the patient may be replaced to ensure 66 patients complete the study. The replacement patients will be assigned the same treatment sequence as the patients to be replaced and will complete that treatment sequence in its entirety. Replacement should not occur beyond 75 patients enrolled, if it is expected to have at least 66 patients complete the study.

Assuming a non-inferiority margin (NIM) of 10%, a 98% treatment success rate for both treatment groups, and a within-patient correlation of zero, 66 completers will provide at least 90% power to show non-inferiority between LY900018 and IMG in treatment success from insulin-induced hypoglycemia with one-sided alpha level of 0.025 based on the Chi-square test.

The proposed NIM of 10% has been chosen based on the previously completed Phase 3 study (Rickels et al. 2016)³.

Final, 01 Feb 2018 Page 8 of 26

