9.4 Pharmacokinetic Assessment

9.4.1 Pharmacokinetic Analysis

Pharmacokinetic parameter estimates will be determined using non-compartmental procedures in validated software program (Phoenix WinNonlin Version 6.4 or later).

Plasma concentrations of glucagon will be used to determine the following PK parameters following LY900018 and GlucaGen administration, when possible:

Final, 01 Feb 2018 Page 12 of 26

Parameter	Units	Definition
AUC(0-4)	pmol.h/L	area under the concentration versus time curve from time zero to 4 hours post-dose
$AUC(0-t_{last})$	pmol.h/L	area under the concentration versus time curve from time zero to time t, where t is the last time point with a measurable concentration
$AUC(0-\infty)$	pmol.h/L	area under the concentration versus time curve from time zero to infinity
$\%$ AUC(t_{last} - ∞)	%	percentage of $AUC(0-\infty)$ extrapolated
C_{max}	pmol/L	maximum observed drug concentration
t_{max}	h	time of maximum observed drug concentration
$t_{1/2}$	h	half-life associated with the terminal rate constant (λz) in non-compartmental analysis
CL/F	L/h	apparent total body clearance of drug calculated after extra-vascular administration
V _z /F	L	apparent volume of distribution during the terminal phase after extra-vascular administration
V _{ss} /F	L	apparent volume of distribution at steady state after extra-vascular administration

The following PK parameters will also be calculated using baseline-adjusted (ie, change from baseline) concentrations of glucagon: AUC, C_{max} , and t_{max} . Baseline glucagon concentrations will be concentrations from samples obtained immediately prior to glucagon dosing (ie, predose).

Additional PK parameters may be calculated, as appropriate. The software and version used for the final analyses will be specified in the clinical study report. Any exceptions or special handling of data will be clearly documented within the final study report.

Formatting of tables, figures and abbreviations will follow the Eli Lilly Global PK/PD/TS Tool: NON-COMPARTMENTAL PHARMACOKINETIC STYLE GUIDE. The version of the tool effective at the time of PK analysis will be followed.

General PK Parameter Rules

- Actual sampling times will be used in the final analyses of individual PK parameters, except for non-bolus pre-dose sampling times which will be set to zero.

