9.5.2 Pharmacodynamic Statistical Methodology

The PD parameters will be statistically analysed, listed and summarized by diabetic type and overall.

The PD parameters (such as BG_{max} and area under the effect concentration-time curve [AUEC]) will be log-transformed prior to analysis and a linear mixed-effects model fitted to the data, with treatment, period, and sequence as fixed effects and patient as a random effect. For each parameter, the treatment difference will be back-transformed to present the ratios of geometric means and the corresponding 90% CI. Similar SAS code will be used as in the PK analysis.

The values of T_{max} will be analyzed nonparametrically using the Wilcoxon signed-rank test. Median differences and approximate 90% CIs for the difference will be calculated for the comparisons of treatments.

Exploratory analyses may be performed for other PD parameters as deemed appropriate.

Final, 01 Feb 2018 Page 17 of 26

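### For PK Tmax, the reported estimate (difference of observed treatment medians) and its signed-rank 90% CI appear to be different quantities, so the estimate can lie outside its own interval

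*SAP*

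**What the plan says.** SAP 9.4.2 names the test for PK Tmax: "The t_{max} will be analyzed using the Wilcoxon signed-rank test". The next sentence sets out what is reported: "Estimates of the median difference based on the observed medians, 90% CIs, and p-values from the Wilcoxon test will be calculated". Protocol 10.3.3.2 has the same sentence. Neither document names a Hodges-Lehmann estimate or any other construction for the interval. SAP 9.4.2 gives example code for the mixed model on log-transformed parameters but none for Tmax.

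The analysis is run at three levels: "The PK parameters will be statistically analysed, listed and summarized by diabetic type and overall". The planned size is 66 completers, with "at least 30 patients with T1DM and T2DM, respectively" (SAP 7).

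The PK rows of the schedule (protocol Section 2) sample at "Predose, 5, 10, 15, 20, 25, 30, 40, 50, 60, 90, 120, 240 min", and SAP 9.4.1 adds: "Actual sampling times will be used in the final analyses of individual PK parameters".

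For PD Tmax, SAP 9.5.2 is worded differently: "Median differences and approximate 90% CIs for the difference will be calculated for the comparisons of treatments". It does not refer to observed medians.

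**The concern.** The signed-rank test works on one difference per patient. Inverting it gives an interval whose limits are ordered Walsh averages, that is, the averages of all pairs of within-patient differences, each difference also being paired with itself. The estimate that belongs to this interval is the median of the Walsh averages, the Hodges-Lehmann estimate.

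The difference between two treatment medians ignores the pairing. When the two Tmax distributions differ in spread or skewness, it also estimates a different population quantity. Nothing forces it into the signed-rank interval.

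Tmax is a listed secondary endpoint under the objective "To characterize the PK profile of 3 mg LY900018 compared to 1 mg IMG", and protocol 10.3.3.1 counts it among the primary PK parameters. The study report could therefore give a treatment difference in time to peak that its own confidence interval excludes.

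**Working it through.** The documents state no Tmax figure, so there is none to reproduce. The check has two parts.

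**1. A fixed example with no distributional assumption.** Take 66 patients with nominal times on the protocol grid. The pairs (treatment A, treatment B) in minutes are (20,10) ×10, (20,15) ×24, (15,10) ×24 and (15,15) ×8.

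- Treatment A has 34 values of 20 and 32 of 15, so its median is 20. Treatment B has 34 values of 10 and 32 of 15, so its median is 10. The difference of medians is 20 − 10 = **10 min**.
- The paired differences are 10 (×10), 5 (×48) and 0 (×8).
- The number of Walsh averages is 66 × 67 / 2 = 2,211.
  - Below 5: 8×9/2 + 8×48 = 36 + 384 = 420.
  - Equal to 5: 48×49/2 + 8×10 = 1,176 + 80 = 1,256.
  - Above 5: 10×11/2 + 10×48 = 55 + 480 = 535.
- The large-sample 90% cut-off is M/2 − 1.645 × √[n(n+1)(2n+1)/24] = 1,105.5 − 1.645 × √(66×67×133/24) = 1,105.5 − 1.645 × 156.5 ≈ 848.
- The 848th value from either end is 5, because 420 and 535 are both below 848. The 90% CI is **5 to 5 min** and the Hodges-Lehmann estimate is **5 min**.

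The reported estimate of 10 min lies outside its interval.

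A second example tests the other reading of the sentence: (15,10) ×30, (20,15) ×4 and (15,15) ×32.

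- Both treatment medians are 15, so their difference is 0.
- The paired differences are 5 (×34) and 0 (×32), so their median is 5.
- The Walsh averages are 0 (32×33/2 = 528), 2.5 (34×32 = 1,088) and 5 (34×35/2 = 595). The 848th from either end is 2.5, so the CI is 2.5 to 2.5 and the Hodges-Lehmann estimate is 2.5.

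Here both candidate estimates, 0 and 5, miss the interval.

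**2. How often, under assumed distributions.** Tmax was drawn as lognormal and snapped to the protocol grid, with 1,500 replicates per scenario. A second run added an assumed ±1 min timing jitter to mimic actual sampling times. Entries are the percentage of trials at n = 66 in which the estimate fell outside the signed-rank 90% CI.

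| Assumed medians (min); log-SDs; correlation | Difference of medians: nominal / jitter | Median of paired differences: nominal / jitter |
|---|---|---|
| 15 v 15; 0.4, 0.4; 0 | 0.7 / 1.6 | 0.7 / 0.8 |
| 15 v 12; 0.4, 0.4; 0 | 10.1 / 15.8 | 2.3 / 3.3 |
| 20 v 12; 0.4, 0.6; 0 | 10.0 / 12.1 | 0.7 / 0.2 |
| 20 v 12; 0.3, 0.8; 0 | 15.5 / 29.1 | 3.4 / 5.3 |
| 20 v 12; 0.5, 0.5; 0.5 | 17.5 / 21.4 | 3.7 / 6.1 |
| 20 v 15; 0.3, 1.0; 0 | 13.2 / 30.7 | 5.5 / 13.9 |

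The Hodges-Lehmann estimate fell outside in 0% of trials in every scenario.

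At n = 30 to 36, the size of a diabetes-type subgroup, the difference of medians fell outside in 1.3% to 8.9% of trials on nominal times and 2.1% to 12.8% with jitter. Further simulations under other assumptions reached about 35%.

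One simulated trial at n = 66 shows the pattern: difference of medians 10 min, Hodges-Lehmann 5 min, 90% CI 2.5 to 7.5 min. The typical distance beyond the limit was about 2.5 min on nominal times and about 1 min or less with jitter.

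**The case against.** The sentence is terse, and the mismatch is inferred. The reference to the Wilcoxon test could attach to the p-values alone, and the median difference could be the median of the within-patient differences. Both are possible, so the point is put as the most natural reading and not as certain. Neither rescues the sentence as written. No other interval method is named, and under the paired-median reading the estimate still misses its interval, less often (0% to about 14% across the simulations). The TFL shells mentioned in SAP 3 are not available here and may say more, but they cannot be assumed to override the SAP sentence.

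The documents do not support three stronger inferences that a reader might draw:

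- **That the estimate can move only in whole sampling steps.** Actual sampling times are used, so the steps are approximate. This does not lower the frequency of misses, but it makes each miss smaller.
- **That PD Tmax has the same defect.** Its text does not mention observed medians, so no mismatch is stated there.
- **That the trial's conclusions are at risk.** The objective is to characterize the PK profile. No margin or success rule uses the Tmax estimate or its interval.

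The small consequence stands as a limit on importance. It does not make the pairing of estimate and interval correct.

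**Conclusion.** The point holds for PK Tmax as a minor correction. On its most natural reading, the plan attaches a signed-rank interval to an estimate that does not belong to it. The fixed example shows, without any distributional assumption, that the two can disagree: 10 min against a 90% CI of 5 to 5.

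The frequency of roughly 1% to 35% of trials depends on assumed Tmax medians, spreads, correlation and timing jitter. The documents give none of these, so the range is not a property of this trial. The misses are small, and typically below one 5-minute sampling interval.

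Only the PK Tmax point estimate is affected. The Wilcoxon p-value, the primary non-inferiority analysis and the sample size stand.

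**What to change.** In SAP 9.4.2, state that the PK Tmax treatment difference is the Hodges-Lehmann estimate of the within-patient difference, reported with its matching signed-rank 90% CI and p-value, overall and by diabetes type. State the direction of subtraction, and show the observed treatment medians as descriptive statistics only. SAP 9.1 already includes medians in its summaries, so nothing is lost.

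Use the same wording for PD Tmax in SAP 9.5.2, for consistency. Record the clarification in SAP 11, because protocol 10.3.3.2 carries the same sentence. Protocol 10.3 allows a change of this kind to be described in the SAP without an amendment if it leaves the principal features alone, as this one does.

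The cost is a few words of SAP text and, if needed, a few lines of code to form and rank the Walsh averages. Data collection, the test and every decision rule stay the same.

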9.5 Pharmacodynamic Assessment

9.5.1 Pharmacodynamic Analysis

Pharmacodynamic parameters will be calculated using NCA Drug Effect Model in validated software program (Phoenix WinNonlin Version 6.4.1 or later) and/or SAS. Key PD parameters will be derived to assess the exposure to glucose and duration of exposure above, below, and within the normal glucose range. The normal range for PG will be considered to be 70 to 108 mg/dL. Actual sampling times will be used for all calculations.

The following PD parameters will be calculated using concentrations of glucose:

Final, 01 Feb 2018 Page 16 of 26

Parameter	Definition
AUECabove	Area under the effect concentration-time curve above the normal range
$AUEC_{below}$	Area under the effect concentration-time curve below the normal range
$AUEC_{within}$	Area under the effect concentration-time curve within the normal range
$AUEC_{0-1.5}$	Area under the effect concentration-time curve from time zero (predose) up to 1.5 hours
BG_{max}	Maximal blood glucose
Duration _{above}	Duration above normal range
Duration _{below}	Duration below normal range
Duration _{within}	Duration within normal range
t_{above}	Time to concentrations above normal range
$t_{ m below}$	Time to concentrations below normal range (after t _{above})
t_{within}	Time to concentrations within normal range
T_{max}	Time to maximum concentration

The following PD parameters will be calculated using baseline-adjusted (ie, change from baseline) concentrations of PG: AUEC_{0-1.5}, BG_{max}, and T_{max}.

Baseline PG concentrations will be concentrations from samples obtained immediately prior to glucagon dosing (ie, time point of 0.00 hour).

If a patient receives additional intervention to raise PG concentrations, measurements taken after the time of intervention will be excluded from the estimation of PD parameters.

Other PD parameters of PG may be calculated if required. Individual concentrations and PD parameters of PG will be summarized with descriptive statistics by treatment.

9.5.2 Pharmacodynamic Statistical Methodology

The PD parameters will be statistically analysed, listed and summarized by diabetic type and overall.

The PD parameters (such as BG_{max} and area under the effect concentration-time curve [AUEC]) will be log-transformed prior to analysis and a linear mixed-effects model fitted to the data, with treatment, period, and sequence as fixed effects and patient as a random effect. For each parameter, the treatment difference will be back-transformed to present the ratios of geometric means and the corresponding 90% CI. Similar SAS code will be used as in the PK analysis.

The values of T_{max} will be analyzed nonparametrically using the Wilcoxon signed-rank test. Median differences and approximate 90% CIs for the difference will be calculated for the comparisons of treatments.

Exploratory analyses may be performed for other PD parameters as deemed appropriate.

Final, 01 Feb 2018 Page 17 of 26

9.5.3 Plasma Glucose Values Statistical Methodology

Descriptive statistics will be used to summarize the baseline, various postdose time points (15, 30, 45, 60, and 90 minutes post glucagon administration), and absolute change from baseline in PG values by treatment group for the FAS.

If a patient receives additional intervention to raise PG concentrations, measurements taken after the time of intervention will be excluded from the analysis.

For this analysis, baseline is defined as the last nonmissing PG measured at the time of or immediately prior to glucagon administration at each treatment visit. A treatment comparison of glucose over the 90 minutes following administration of glucagon will be completed using a linear mixed model with repeated measures (MMRM) that accounts for the correlation due to the crossover design and the correlation due to multiple measures. The baseline score, treatment period, time points and their interaction will be included as covariates in the model. Least-square means and 2-sided 95% confidence limits will be calculated for the difference in PG between treatment groups (IMG minus NG) at each time point.

In the MMRM model, the within-patient errors are modelled as an unstructured variance-covariance matrix. If the analysis fails to converge, the following variance-covariance matrix will be used (in the order listed) until one converges:

- 1. Heterogeneous Toeplitz (TOEPH)
- 2. Heterogeneous First-order Autoregressive (ARH[1])
- 3. Heterogeneous Compound Symmetry (CSH)
- 4. Toeplitz (TOEP)
- 5. First-order Autoregressive (AR[1])
- 6. Compound Symmetry (CS)

The Kenward-Roger approximation will be used to estimate denominator degrees of freedom for the MMRM models.

Below is the example SAS code performing the MMRM analysis:

```
proc mixed data=c;
class patient time visit treatment;
model value = treatment time visit baseline treatment*time /solution
ddfm=kr;
repeated time(visit)/subject=patient type=un;
lsmeans treatment*time/cl diff om;
run;
```

As an exploratory analysis and if there is sufficient data, a subgroup analysis of plasma glucose over time by concomitant oral diabetes drug will be performed (with particular focus on Sulfonylureas). The purpose of the analysis is to assess whether the concomitant oral diabetes

Final, 01 Feb 2018 Page 18 of 26

drug triggers rebound hypoglycaemia or not. For each concomitant oral diabetes drug, the data will be summarized by treatment and diabetes type.

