9.6.10 Nasal and Non-nasal Score Questionnaire

The scoring for each response to the Nasal and Non-Nasal Score Questionnaire will follow the scale displayed on the questionnaire ('None'=0, 'Mild'=1, 'Moderate'=2, 'Severe'=3). The total score of the questionnaire will be calculated as the sum of the scores for each question. Descriptive statistics will be used to summarize the baseline, various postdose time points (15, 30, 60, and 90 minutes), and absolute change from baseline in total score of Nasal and Non-Nasal Score Questionnaire by treatment group.

For this analysis, baseline is defined as the score measured prior to glucagon administration at each treatment visit.

The total score will be compared between treatment groups through a linear MMRM that accounts for the correlation due to the crossover design and the correlation due to repeated measures of the questionnaire. The MMRM analysis of nasal symptom score will be performed using the similar approach as specified in the plasma glucose analysis.

The number and proportion of patients within each score categories of each question in the Nasal and Non-Nasal Score Questionnaire in increasing severity (none, mild, moderate, and severe) at each time point and shift of categories from baseline to maximal (and last) postdose severity category will be provided by treatment group.

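### The fallback covariance structures for the glucose MMRM do not separate within-visit from between-visit correlation, so if one is used the 95% limits can be too narrow or too wide

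*SAP*

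**What the plan says.** SAP section 9.5.3 compares plasma glucose over the 90 minutes after dosing and reports IMG minus nasal glucagon, with two-sided 95% limits, at each time point. It states that the model is meant to handle both the crossover correlation and the correlation among repeated samples.

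First choice: "the within-patient errors are modelled as an unstructured variance-covariance matrix". The example code has "repeated time(visit)/subject=patient type=un", so both visits sit in one matrix per patient.

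Fallback: "If the analysis fails to converge, the following variance-covariance matrix will be used (in the order listed) until one converges". The list is TOEPH, ARH(1), CSH, TOEP, AR(1), CS. Degrees of freedom are Kenward-Roger. No robust standard error is named, and no code is given for any fallback.

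The rule reaches further than glucose. Section 9.6.10 says "The MMRM analysis of nasal symptom score will be performed using the similar approach as specified in the plasma glucose analysis", and section 9.6.11 analyses the Edinburgh scale in the same way as the nasal questionnaire. Protocol section 5.4 sets the washout between visits at 3 to 14 days.

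**The concern.** An unstructured matrix can describe any pattern across two visits, so putting both visits in one block does no harm there. The fallbacks are different: each describes a single series and has no separate visit dimension.

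- TOEPH, ARH(1), TOEP and AR(1) make correlation depend on distance along the series. If levels run visit 1 times and then visit 2 times, 90 minutes at visit 1 and 15 minutes at visit 2 are treated as neighbouring samples although days separate them. The same clock time at the two visits is five steps apart.
- CSH and CS have no ordering, so they create no false neighbours. Their fault is a single correlation for all pairs, within and between visits.

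The treatment difference at a given time is a between-visit contrast within patient. Its standard error therefore depends directly on the between-visit correlation, which is what the fallbacks cannot estimate separately. Kenward-Roger adjusts inference under the assumed structure and does not repair a wrong one. At stake are the 95% limits at each time in the glucose, nasal and Edinburgh comparisons, if a fallback is used.

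**Working it through.** The documents state no figure on this point, so there is none to reproduce.

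**Inputs.** From the documents: the structures, the patient-level block and the five times 15, 30, 45, 60 and 90 minutes (SAP 9.5.3); 66 completers (SAP 7), taken as 33 per sequence. Fixed effects follow the example code, without baseline. Assumed: SDs, correlations, and level order visit then time.

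**Step 1: what shares a lag.** With 5 times × 2 visits there are 10 positions. For lags L = 1 to 5 there are 2(5 − L) within-visit pairs and L cross-visit pairs:

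| Lag | Within-visit | Cross-visit |
|---|---|---|
| 1 | 8 | 1 |
| 2 | 6 | 2 |
| 3 | 4 | 3 |
| 4 | 2 | 4 |
| 5 | 0 | 5 (same time, two visits) |

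Toeplitz forces one value on each row. AR(1) also ties lag 5 to lag 1: a parameter of 0.9 implies 0.9^5 = 0.59 between visits at the same time, and 0.6 implies 0.6^5 = 0.08.

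**Step 2: direction of the error, by hand for CS.** With balanced sequences and equal SDs, the estimate at one time is the mean within-patient difference, with variance 2σ²(1 − r)/n, where r is the same-time between-visit correlation. CS replaces r by ρc, the mean of all 10 × 9/2 = 45 pairwise correlations. So

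SE ratio (model/true) = √[(1 − ρc)/(1 − r)], and coverage = 2Φ(1.96 × ratio) − 1.

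In 15-minute units the five times have gaps 1 (3 pairs), 2 (3), 3 (2), 4 (1) and 5 (1). Correlation is given per 15 minutes, and cross-visit correlation is r times the within-visit value.

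- Within 0.9, between 0: per visit 3(0.9) + 3(0.81) + 2(0.729) + 0.6561 + 0.5905 = 7.835; two visits 15.669. ρc = 15.669/45 = 0.348. Ratio √0.652 = 0.807; coverage 88.6%, too narrow.
- Within 0.6, between 0.6: per visit 3(0.6) + 3(0.36) + 2(0.216) + 0.1296 + 0.0778 = 3.519; two visits 7.039. Cross-visit 0.6 × (5 + 7.039) = 7.223. ρc = 14.262/45 = 0.317. Ratio √(0.683/0.4) = 1.307; coverage 99.0%, too wide.

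**Step 3: all six structures.** Parameters were chosen to minimise log|V| + tr(V⁻¹S) against the assumed true S, and the model-based SE was compared with the true (sandwich) SE. Coverage of a nominal 95% interval across the five times:

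| Structure | 0.9 / 0 | 0.6 / 0.3 | 0.6 / 0.6 |
|---|---|---|---|
| TOEPH | 87–91% | 93–95% | 93–96% |
| ARH(1) | 81–87% | 97–98% | over 99% |
| CSH | 88–89% | 96–97% | 99% |
| TOEP | 87–89% | 93–95% | 94–95% |
| AR(1) | 84–86% | 97–98% | over 99% |
| CS | 89% | 96% | 99% |

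A simulation of 300 replicates agrees: at 0.9 / 0, AR(1) 81–85% and CS 85–89%; at 0.6 / 0.6, AR(1) 99–100% and CS 98–99%.

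**Step 4: a middle range.** Within-visit correlation 0.7 to 0.9 between successive times, between-visit 0.2 to 0.4, equal SDs. If cross-visit correlation decays with lag as within-visit correlation does, TOEPH covers about 84–93% and TOEP 80–93% (SE 8–35% too small). If it is constant, TOEP covers about 87–95%, and TOEPH also reaches about 95% at the top. AR(1) covers about 84–97.5%; at 0.7 / 0.4 it is 95–97.5%, so its limits there are nominal to too wide.

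**Step 5: unequal SDs.** With SD rising from 10 to 32 mg/dL (assumed), the homogeneous structures TOEP, AR(1) and CS are generally too wide at 15 minutes and too narrow at 90. For AR(1) in the 0.9 / 0 case the SE ratio goes from 1.21 to 0.58.

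**The case against.** The planned model is unstructured, and if it converges nothing here applies. No success criterion rests on these limits: the primary non-inferiority test is PROC TTEST on paired differences (SAP 9.3.1). Both points stand and keep this minor.

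The code is labelled as an example and shows the REPEATED line only with an unstructured matrix, where level order is irrelevant. Reusing it unchanged for the fallbacks is the natural reading, but an inference. If levels were sorted by time first, the false adjacency would not arise; in the cases tried, TOEPH, ARH(1) and AR(1) then covered about 94–97%.

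The five times are listed for the descriptive summary, not explicitly for the MMRM. The protocol schedule has no 45-minute glucose sample (it has 40 and 50). Four usable times would give 8 × 9/2 = 36 unstructured parameters, five give 10 × 11/2 = 55, and all ten scheduled postdose samples to 90 minutes give 20 × 21/2 = 210. With ten times the errors are larger in both directions (coverage about 66% to 100%).

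Three stronger readings are tempting, and the documents do not support them:

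- That a fallback always makes the limits too narrow. The table shows both directions, and with unequal SDs the direction can change between time points.
- That all six structures join the two visits end to end. CSH and CS have no ordering.
- That non-convergence is likely for the questionnaires because scores cluster at the bottom. No score distribution is given. Reporting by diabetes type (SAP 9.1), with a target of at least 30 completers each, would make failure more plausible if the MMRM is fitted by type, but the SAP does not say that it will be.

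**Conclusion.** The point holds in a limited form. All six fallbacks fail to separate within-visit from between-visit correlation, so the list does not meet the SAP's own aim for the model. Four of the six also impose a false adjacency between visits, provided levels run visit then time. If the unstructured fit fails, the 95% limits can err either way: too narrow when within-visit correlation is high relative to between-visit correlation, and near nominal or too wide when between-visit correlation is substantial or within-visit correlation decays quickly. TOEPH, tried first, covered about 84–95% in the middle range.

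These sizes rest on assumed correlations, equal SDs except where stated, 33 patients per sequence, five times per visit and no baseline covariate. The matter is a refinement of a secondary analysis and of the questionnaire comparisons. It gives no ground for doubting the primary result.

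**What to change.** Replace the fallback list in SAP 9.5.3, and by reference in 9.6.10 and 9.6.11, with structures that keep visit and time separate and let the variance differ over time:

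1. A direct product UN@UN, visit by time. For five times it has 3 + 15 − 1 = 17 parameters against 55.
2. If that fails, a patient random effect with a heterogeneous time structure within subject=patient*visit.
3. For any simpler structure, a sandwich (empirical) standard error, with its degrees of freedom stated, because Kenward-Roger belongs to the model-based variance.

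Do not use UN@AR(1) or UN@CS with model-based standard errors: they assume equal variance over time. UN@AR(1) gave 95.0% coverage in separable cases with equal SDs. With the SD rising about threefold, its SE is about 2.3 times too large at 15 minutes and 28% too small at 90. UN@UN removes that problem but still assumes that cross-visit correlation follows the within-visit pattern; the second structure covers a constant between-visit covariance.

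State the level order and the time points that enter the model. The cost is one SAP list and one code line. The downside is the sandwich estimator's known weakness in small samples, which matters more if the model is fitted by diabetes type.
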